5.2.3 Socioeconomic variables

- Educational level
- Marital status
- Living situation
- Occupation status
- Sick leave
- Income level
- Income source (salary/sick pension)
- Country of birth

6. ETHICAL CONDUCT OF THE NON-INTERVENTIONAL STUDY

The DBA will be performed in accordance with ethical principles that are consistent with the Declaration of Helsinki, ICH GCPs and the applicable legislation on Non-Interventional Studies.

6.1 Ethics review

The final protocol of the DBA must be approved or given a favourable opinion in writing by the Ethics Committee. The Ethics Committee must also approve any amendment to the protocol, according to local regulations.

After an approval from the Ethics committee, the NBHW and SCB also make an independent evaluation of the data request.

6.2 Subject Informed consent

Normally, informed consent is needed when either the research imposes a risk for patients or the study requires data containing personal identifiers. Studies conducted entirely using administrative databases and which do not use any personal identifiers may require only abbreviated review or may not require formal review at the discretion of the Ethics Committee.

6.3 Subject data protection

The merging of data from the registers will be performed by the NBHW. No identification of patients will be possible elsewhere.

7. STUDY MANAGEMENT

7.1 DBA timetable and end of study

Before any data retrieval is initiated the following should be fulfilled

- Written approval of the DBA by the Ethics Committee, according to local regulations
- Proper agreements between AstraZeneca and National Board of Health and Welfare (Socialstyrelsen) are signed

The planned timetable for the DBA is estimated to be as follows:

• First data collection: Q4 2011

Data base Audit Study Protocol DBA Code VD-NS-1101 Edition Number 1.0

Last data collection: Q4 2011

• Data Base Audit report: Q1 2012

Should AstraZeneca decide to discontinue the study prior to what was established in this protocol, the investigator, and relevant authorities should receive written notice describing the reasons why the study was terminated at an earlier date.

8. DATA MANAGEMENT

8.1 Collection, monitoring, processing of data and archiving

Please see section 3.2 for details regarding data collection.

The anonymous databases with the merged data will be hosted at Psykiatri Nordväst, Karolinska sjukhuset and by the institution doing the statistical analysis. Data Management and statistical analysis of data will be managed by AstraZeneca (or external service provider contracted by AstraZeneca).

8.2 Reporting and publication of data

AstraZeneca will ensure analysis and aim to publish the results in a scientific paper and/or scientific congress. Authorship will be according to the principal criteria for eligibility that are detailed in the Uniform Requirements for Submission of Manuscripts to Biomedical Journals (ICMJE, 5th Edition, 1997).

9. STATISTICAL METHODS AND SAMPLE SIZE DETERMINATION

9.1 Statistical evaluation – general aspects

A DBA is a study in which epidemiological methods including other methods that can be used to analyse human population health data.

The principal features of the planned statistical evaluation will involve descriptive statistics analysis the different populations.

The descriptive analysis (both for the primary and secondary objectives) will for the continuous variables be done by calculating mean, standard deviation, 95% CI, number of observations, minimum, maximum, median and number of missing observation and for categorical variables number of observations, frequencies and percentage.

Data base Audit Study Protocol DBA Code VD-NS-1101 Edition Number 1.0 Date

The analysed variables at the index date will be age, gender, educational level, marital status, living situation, occupation status, sick leave, income level, income source (salary/sick pension), country of birth, co-morbidities (as specified in section 5), co-medications (as specified in section 5).

The prescribers occupation, education and specialist code will be analysed, ownership (private/public) and country divided in quetiapine IR and quetiapine XR.

The variables analysed before the index date will be; number of hospital stays and sum of length of hospital stays.

The treatments after the index date will be analysed for the following variables: duration, dosage, drugs switches, DDD per package, number of prescribed packages for quetiapine IR/XR and co-medications including dosage and duration of these co-medications.

Attempts will be made to find the prescribed dose and the diagnosis from the free text on the prescription label on the drug for quetiapine IR and quetiapine XR either by text mining or by manually go through the different prescription labels.

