2. DBA OBJECTIVES

2.1 Primary objective

The primary objective of the study is to describe the detailed clinical treatment (including duration of treatment, doses, drug switches, and add-on therapy), in patients with BD and on treatment with quetiapine XR and/or quetiapine IR before, at and after the index date.

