2.2 Secondary objectives

- 1. To describe co-morbidity, demographics, sick leave, early retirement and socioeconomic factors in patients with BD and on treatment with quetiapine XR and/or quetiapine IR before and at the index date.
- 2. To describe the detailed clinical treatment (including duration of treatment, doses, drug switches, and add-on therapy) in patients with BD, including all drug treatment after the index date.
- 3. To describe co-morbidity, demographics, sick leave, early retirement and socioeconomic factors in patients with BD, including all drug treatment before and at the index date

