3.1 Study Design

This is an epidemiological registry study on all patients who have been hospitalised in Sweden at least once since 1987 with a diagnosis during hospitalisation of BD and/or schizophrenia spectrum disorder. Index visit (baseline) is defined as the date when a patient dispensed their first prescription of quetiapine XR and/or quetiapine IR. Patients with index visit between 1st of January 2009 and 31st of December 2010 will be more detailed described, and data will be collected six months prior to the first dispensed prescription of quetiapine XR and/or quetiapine IR. Patients started their treatment with quetiapine XR and/or quetiapine IR before 1st of January 2009 will have 1st of January 2009 as index visit.

May 2008 quetiapine XR was launched for the indications schizophrenia and bipolar mania in Sweden and March 2009 quetiapine XR and IR was launched in bipolar depression.

Data on patients with schizophrenia spectrum disorder will be collected in order to allow us to exclude patients who have been re-diagnosed to or from bipolar disorder. The latest diagnose is defined as the patients diagnose, i.e. if a patient gets a schizophrenia spectrum disorder diagnose after diagnose of bipolar disorder, the patient will not be included in the study.

Figure 1 Patient flow

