5.2.1 Co-morbidities

- Ischemic heart disease
 - ICD-9: 413
 - ICD-10: I 20.9, I 25.1
- Peripheral arterial disease including extra cerebral, non-coronary arterial thromboembolism
 - ICD-9: 440,441,444
 - ICD-10: I70- I79
- Chronic obstructive pulmonary disease (COPD)

- ICD-9: 496
- ICD-10: J44.9
- Psychiatric admission history including number of previous admissions.
 All F psychiatric (diagnosis) will be collected, with special interest of diagnoses
 specified see Table 3-4. All V, X and Y diagnosis (External causes of morbidity and mortality) are included, see appendix B, Translator ICD10 to ICD9.
- Drug and alcohol abuse
 - ICD-9; 305.0, 291.89, 292, 305.00-305.93, 304.00-304.93
 - ICD-10: F10-F19
- Cancer
 - ICD-9: 140-209
 - ICD-10: C00-C99
- Endocrine disease
 - ICD-9: 240-246
 - ICD-10: E16-E99
- Diabetes mellitus
 - ICD-9: 250
 - ICD-10: E10-E11
- Neurological
 - ICD-9.: 320-389
 - ICD-10: G00-G99 (excluding G45)
- Heart failure
 - ICD-9: 428
 - ICD-10: I 50
- Myocardial Infarction
 - ICD-9. 410, 429
 - ICD-10: I 21-22

- Stroke and TIA
 - ICD-9: 430-438
 - ICD-10: I 60-69
- Hypertension
 - ICD-9: 401
 - ICD-10: I 10
- Renal failure
 - ICD-9: 586, 403, 404, 639.3
 - ICD-10: N 17-19
- Intoxication
 - ICD9: 960-979
 - ICD10: T4n

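### The primary objective covers treatment before the index date, but the pre-index analysis in Section 9.1 lists only hospital stays and Section 5.2 leaves out pre-index co-medication

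*Protocol*

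**What the plan says.** Protocol 2.1 sets the primary objective as to "describe the detailed clinical treatment (including duration of treatment, doses, drug switches, and add-on therapy), in patients with BD", for patients "on treatment with quetiapine XR and/or quetiapine IR before, at and after the index date".

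Protocol 2.2, secondary objective 1, asks for co-morbidity, demographics, sick leave, early retirement and socioeconomic factors in patients "on treatment with quetiapine XR and/or quetiapine IR before and at the index date". Objective 3 asks for the same in all patients with bipolar disorder, over the same two periods. Objective 2 repeats the treatment wording of 2.1 but is limited to the time after index.

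Protocol 9.1 states that the descriptive analysis serves the primary and the secondary objectives, and then lists variables period by period:

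- Before index: "The variables analysed before the index date will be; number of hospital stays and sum of length of hospital stays".
- At index: age, gender, the socioeconomic variables including sick leave, and "co-morbidities (as specified in section 5), co-medications (as specified in section 5").
- After index: duration, dosage, switches, package information, and co-medications with their dosage and duration.

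Protocol 5.2 places the co-morbidities of interest before quetiapine treatment, but the co-medications of interest only from the index visit onwards.

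Protocol 3.1 adds that "data will be collected six months prior to the first dispensed prescription" of quetiapine, and that patients who started quetiapine before 2009 receive 1 January 2009 as their index date.

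**The concern.** The pre-index sentence in 9.1 is worded as a complete list and contains no drug variable. An analyst who follows it would produce no table of earlier treatment, although the primary objective names that period. Section 5.2 does not repair this, because it too leaves pre-index co-medication out.

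Two things are at stake. For new users, the pre-index record shows which drugs the patient was on and whether they were kept or replaced when quetiapine began. That bears on the rationale in 1.2, where XR is thought to serve as foundation treatment and IR as a lower-dose addition. For patients who started before 2009, index is an assigned calendar date and not a treatment start, so duration counted from index leaves out all their earlier quetiapine use.

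**Working it through.** The protocol gives no figure to reproduce, so the check sets the objectives against the variable lists.

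**Primary objective (2.1) against 9.1**

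| Element in 2.1 | Before index | At index | After index |
|---|---|---|---|
| Duration | not listed | not listed | listed |
| Doses | not listed | not listed | listed |
| Switches | not listed | not listed | listed |
| Add-on therapy | not listed | co-medications | co-medications |
| Elements covered | 0 of 4 | 1 of 4 | 4 of 4 |

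**Secondary objectives 1 and 3 against 9.1 and 5.2**

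| Item | Before index | At index |
|---|---|---|
| Co-morbidity | covered: 9.1 points to Section 5, and 5.2 places it before treatment | listed |
| Sick leave | not listed | listed |
| Socioeconomic variables | not listed | listed |
| Early retirement | not named | not named; nearest item is income source (salary or sick pension) |

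**Is the mention of the pre-index period a slip?** Probably not. Secondary objective 2 uses the same treatment wording with only the post-index period, so the authors distinguished the periods. Section 3.1 also provides for data from before the first dispensing.

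**Does another reading of 2.1 close the gap?** Suppose that "before, at and after the index date" qualifies being on quetiapine and not the description of treatment. Patients who started before 2009 still have quetiapine treatment before their assigned index, and 9.1 does not analyse it. New users have no earlier quetiapine by definition, so for them pre-index treatment means other drugs, which 5.2 and 9.1 both omit. The gap remains on either reading.

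**Are there data to fill it?** The drug register starts on 1 July 2005 (3.3.2).

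- The earliest index date is 1 January 2009. Six months earlier is 1 July 2008, three years after the register opened, so every patient's six-month window lies inside it.
- For patients assigned 1 January 2009, observable earlier quetiapine use reaches back at most from 1 January 2009 to 1 July 2005, which is 3.5 years. XR was launched in May 2008 (3.1), so earlier XR use can span at most about 8 months (May to December 2008).
- Index years are 2009 and 2010, so the preceding calendar years are 2008 and 2009. LISA is available at least from 1990 (3.3.4).

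**The case against.** The strongest defence is that a protocol need not list every table, and that a statistical analysis plan, which is not shown, may add pre-index treatment. It is therefore too strong to infer that this treatment will never be analysed. What stands is narrower: the protocol does not leave the matter open, because it fixes a pre-index list that disagrees with its own primary objective.

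It can also be said that post-index switches may reveal the drug switched from, and that co-medications at index already show concurrent use. Both are fair. A reader might infer that the foundation versus add-on question cannot be answered without pre-index data. The protocol does not support that, since add-on use is concurrent treatment and is covered at index and afterwards. What stays missing is the dose, duration and accompanying therapy of earlier treatment, and a direct view of what was continued or replaced.

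A further tempting reading is that the six months in 3.1 conflict with "Psychiatric admission history including number of previous admissions" in 5.2.1, so that most co-morbidity and admission history would be lost. The text does not say so. Section 3.1 does not apply the six months to diagnoses or admissions and gives no purpose for those data. Sections 5.1 and 5.1.1 draw on patients hospitalised at any time since 1987 and list admission dates and diagnoses without a window, and 5.2.1 gives ICD-9 codes. These point to the full patient register history. At most the look-back could be stated more clearly, and no share of lost history can be calculated.

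**Conclusion.** The mismatch is real. In the analysis that this protocol sets out, none of the four treatment elements of the primary objective is covered before index, and Sections 5.2 and 9.1 share the omission. For secondary objectives 1 and 3 the gap is limited to sick leave, socioeconomic factors and early retirement. Pre-index co-morbidity is not part of it.

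The conclusion rests on reading the pre-index sentence in 9.1 as complete, which is its plain sense. The number of patients affected cannot be given, because the protocol does not say how many of the expected 14,000 to 16,000 started quetiapine before 2009. The point should be corrected so that the primary objective is answered in full. It does not call the design or the data sources into question.

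**What to change.** Either extend the analysis or narrow the objectives.

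**To extend it**, amend both 5.2 and 9.1:

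1. Add pre-index dispensing of the 5.2.2 drug classes and, for patients who started before 2009, of quetiapine by formulation. Report any use, dispensed amount or dose, duration, and whether the drug was continued, stopped or replaced at index.
2. Use the six months before index as look-back. For new users this is the window in 3.1, because index is the first dispensing. For patients assigned 1 January 2009 the two dates differ, so anchor the window to 1 January 2009.
3. Report patients assigned 1 January 2009 separately from new users. Take their quetiapine duration from the first dispensing in the drug register, noting that it is a minimum for anyone already treated in July 2005.
4. Add sick leave, early retirement and the socioeconomic variables from the LISA record of the calendar year before index. Say how early retirement is defined, since neither 5.1.4 nor 9.1 names it.
5. Note under the tables that the drug register holds no in-patient drug use (3.3.2).

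**To narrow it**, remove *before* from 2.1, and from secondary objectives 1 and 3 for the items that will be described at index only.

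The cost is revised wording and additional descriptive tables. The drug register and LISA data are already requested and 5.1 sets no date limit on them. It should be confirmed that the extract reaches back to July 2005 and includes the LISA years 2008 and 2009.

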3.3 Data sources

3.3.1 National Patient Register

NPR includes all in-patient care in Sweden from 1987. From 2001 the register also contains information on outpatient visits at hospitals, including day surgery carried out by both private

Data base Audit Study Protocol DBA Code VD-NS-1101 Edition Number 1.0 Date

and public caregivers. Information on primary care visits or open care visit outside hospital are not included in the NPR. The information in NPR can be divided into four different groups

- 1. Patient data (personal registration number (PIN), sex, age, place of residence)
- 2. Geographic data (county council, hospital/clinic, department)
- 3. Administrative data (dates of admission and discharge, length of stay for inpatients, acute/planned admission, admitted from, discharged to) and
- 4. Medical data (the main diagnosis, secondary diagnoses, external cause of injury and poisoning, procedures and surgery).

Before 1997 the register contained a total of six diagnoses per admission, increasing to eight in 1997 and since 2009 an unlimited number of secondary diagnoses can be recorded.

At present, the NPR is updated once a year and normally available in September-October for the preceding year. The missing data on PIN for 2007 has been estimated to less than one percent.

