3.3.3 Population Register

To ascertain a correct population at risk time in the data analysis, information on dates of emigration and death for all patients will be retrieved from the Register of Population at Statistics Sweden.

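### Treatment duration and switching, both in the primary objective, are given plain summaries with no handling of treatment still ongoing when the data end

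*Protocol*

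**What the plan says.** The primary objective (Protocol 2.1) is to "describe the detailed clinical treatment (including duration of treatment, doses, drug switches, and add-on therapy), in patients with BD".

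Protocol 9.1 opens its methods with "The descriptive analysis (both for the primary and secondary objectives" and says the analysis will "for the continuous variables be done by calculating mean, standard deviation, 95% CI, number of observations, minimum, maximum, median and number of missing observation". Categorical variables get counts, frequencies and percentages. A later sentence of the same section reads "The treatments after the index date will be analysed for the following variables: duration, dosage, drugs switches", followed by package variables and co-medications. The section contains no time-to-event summary, no rate per person-time and no rule for treatment that has not ended.

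On timing, Protocol 3.1 says "Patients with index visit between 1st of January 2009 and 31st of December 2010 will be more detailed described", and patients who started earlier get 1 January 2009 as their index date. Protocol 7.1 puts first and last data collection in Q4 2011. The last date of dispensing follow-up is not given.

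Protocol 3.3.3 explains the population register request: "To ascertain a correct population at risk time in the data analysis, information on dates of emigration and death" are to be retrieved. Section 9.1 describes no analysis that uses them.

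**The concern.** A patient still on quetiapine when the data end has a duration known only to exceed what was observed. Index dates span 24 months and extraction is a single event, so the time available to observe the end of treatment differs between patients by up to two years. A plain mean that counts ongoing treatment as ended understates persistence. Setting ongoing patients to missing also favours short treatments. The percentage who switch or receive add-on therapy has the same weakness, because patients indexed late have had less time to do either.

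These quantities are the main product of a purely descriptive study. The 95% CI gives no warning: with the expected sample size it would be narrow around a value that partly reflects the calendar rather than the treatment.

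**Working it through.** The protocol gives no expected duration or censored share, so there is no figure of its own to reproduce. What follows is an illustration under stated assumptions.

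**Inputs from the protocol**
- Index window: 1 January 2009 to 31 December 2010, 24 months (3.1).
- Extraction: Q4 2011 (7.1).
- The Prescribed Drug Register is updated monthly (3.3.2). The National Patient Register is "normally available in September-October for the preceding year" (3.3.1), so at extraction it normally reaches the end of 2010.
- Expected size: 14,000 to 16,000 (9.2).

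**Assumptions**
- Time on treatment T is exponential with true mean m = 6, 12 or 24 months.
- New starters enter uniformly over the window.
- Dispensing data end either on 31 December 2010 (follow-up C uniform on 0 to 24 months) or on 30 September 2011 (C uniform on 9 to 33 months).

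**Plain mean for new starters, ongoing treatment counted as ended**

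For C uniform on (a, a+24): E[min(T,C)] = m − (m²/24)(e^(−a/m) − e^(−(a+24)/m)).

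For m = 12 and a = 0: 12 − 6(1 − 0.1353) = 6.81. For m = 12 and a = 9: 12 − 6(0.4724 − 0.0639) = 9.55.

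| True mean | Cut December 2010 | Cut September 2011 |
|---|---|---|
| 6 | 4.53 (−25%) | 5.67 (−5.5%) |
| 12 | 6.81 (−43%) | 9.55 (−20%) |
| 24 | 8.83 (−63%) | 13.57 (−43%) |

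Under this model the relative shortfall equals the share still on treatment at data end.

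**Plain median.** The observed median solves e^(−x/m) × P(C > x) = 0.5; the true median is m ln 2 = 4.2, 8.3 or 16.6 months.
- December 2010 cut: P(C > x) = 1 − x/24, giving 3.3, 5.3 and 7.6 months, all low.
- September 2011 cut: everyone has at least 9 months of follow-up, so true medians of 4.2 and 8.3 are unaffected. For m = 24, e^(−x/24)(33 − x)/24 = 0.5 gives 12.7 against 16.6.

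So the median is protected only when it is shorter than the shortest follow-up.

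**Precision.** In a simulation with m = 24, a December 2010 cut and 7,000 patients per formulation (an assumed even split), the half-width of the 95% CI was 0.16 to 0.19 months. Plain means were 9.4 and 11.9 months for assumed shares of reset patients of 10% and 50%. Total time divided by number of stops gave 23.8 in both, close to the true 24.

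**XR against IR.** A patient indexed on 1 January 2009 has C fixed at 24 or 33 months. With m = 12 the expected plain mean is 12(1 − e^(−2)) = 10.38 or 12(1 − e^(−2.75)) = 11.23. Suppose 10% of XR users and 50% of IR users are reset patients, with identical persistence:
- m = 12: 7.2 against 8.6 months (December 2010), 9.7 against 10.4 (September 2011).
- m = 24: 9.5 against 12.0 months (December 2010), 14.0 against 15.8 (September 2011).

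Extending the range of m to 48 months, the gap runs from about 0.1 to 3.5 months. The 10% and 50% are assumptions; the protocol gives no shares.

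**The case against.** **Section 9.1 does not explicitly tie a statistic to duration.** The summaries stand in one sentence and the post-index variables in another, and the section is headed general aspects. Censoring rules and data cuts are commonly left to a statistical analysis plan, and 3.3.3 shows that time at risk was considered. This lowers the severity but does not remove the point. Duration is continuous, the summaries are stated to cover the primary objective, and a plan that followed 9.1 faithfully would carry the problem over.

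**The larger bias figures need an early cut.** Duration comes from dispensing data, which are updated monthly; the yearly lag belongs to the patient register. No passage stops dispensing follow-up at December 2010. This stands, so the September 2011 column deserves at least equal weight.

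**A reader might infer that many patients are still on treatment and that the plan will create a false XR–IR difference.** The documents do not establish either. Long-term treatment (1.1) and late entry make a substantial ongoing share plausible, but no share is given. XR was launched in May 2008, so it too has patients reset to 1 January 2009, and the bipolar depression launch of both formulations in March 2009 falls inside the window. Section 1.2 also rules out an outcome analysis between formulations. A differential bias could therefore mislead a side-by-side description but would not corrupt a planned test.

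**A reader might also infer that every duration is biased low.** For reset patients that does not follow. Discarding time before 1 January 2009 shortens durations, while sampling people already on treatment over-represents long users. The exponential model is memoryless and cannot show this second effect.

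**Conclusion.** The point holds for new starters. The protocol prescribes plain summaries for primary-objective quantities that its own design censors, and it states neither an end of follow-up nor a rule for ongoing treatment, death or emigration. Under exponential persistence with true means of 6 to 24 months and uniform entry, the plain mean is low by about 5.5% to 43% with data to September 2011 and by 25% to 63% with data to December 2010. The plain median is low in every December 2010 case, and in the September 2011 case once the true median exceeds the 9-month minimum follow-up.

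A difference in bias between XR and IR is possible but conditional on an entry mix the documents do not report. For patients reset to 1 January 2009 the net direction is unknown, which is itself a reason not to pool them with new starters.

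**What to change.** 1. State the last date of dispensing follow-up.
2. For duration, replace the plain summaries by Kaplan-Meier time to discontinuation: median and 6- and 12-month persistence, or a restricted mean to a fixed horizon.
3. For switch and add-on, replace crude percentages by cumulative incidence or rates per person-time.
4. Censor at data end and at emigration. State how death is handled; for switching, treat it as a competing event.
5. Report new starters separately from patients whose index was reset to 1 January 2009, within each formulation.
6. If inpatient days are used to bridge dispensing gaps (the Prescribed Drug Register omits inpatient drugs), limit this to the period the patient register covers.

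The cost is revised wording in 9.1 and a little more analysis with standard software. Dispensing, emigration and death dates are already requested; no new data source is needed.
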